5.3 Prohibited Medications and Therapy

Subjects must be able to safely discontinue any prohibited medications as specified in Section 5.1 and Section 5.4. Subjects must be consented for the study prior to discontinuing any prohibited medications for the purpose of meeting study eligibility.

The following medications are prohibited through the end of study drug administration:

- All biologic therapies used for the treatment of CD or with potential for additive immunosuppressive effect including but not limited to the following (including biosimilars): abatacept (Orencia®), adalimumab (Humira®), anakinra (Kineret®), belimumab (Benlysta®), certolizumab pegol (Cimzia®), etanercept (Enbrel®), golimumab (Simponi®), infliximab (Remicade®), natalizumab (Tysabri®), rituximab (Rituxan®), tocilizumab (Actemra®), ustekinumab (Stelara®), vedolizumab (Entyvio®), and risankizumab (Skyrizi®).
- Investigational agents
- All other therapies with a potential therapeutic impact on CD (except for those allowed per protocol) including but not limited to the following: Janus kinase (JAK) inhibitors such as tofacitinib, cyclosporine, tacrolimus, or mycophenolate mofetil.
- Live vaccination (see Section 5.4).
- Rectal therapy, with the exception of those required for endoscopy.
- IV, intramuscular, intra-articular, epidural, intra-bursal, intra-tendon sheath, trigger or tender point, or rectal administration of glucocorticoids;
- Super high potency and/or high potency topical glucocorticoids (see Operations Manual [Appendix F], Section 3.5). From Weeks 0 to 28 of the Maintenance Period super high potency and/or high potency topical glucocorticoids are permitted for non-CD-related adverse events.
- Corticotropin gel injection (e.g., Acthar®)
- Apheresis (e.g., adacolumn apheresis).
- Exclusive enteral nutrition or any parenteral nutrition.
- NSAIDs with the exception of low dose aspirin daily and selective COX-2 inhibitors.
- Traditional oral Chinese medicine (e.g., tripterygium glycosides, sinomenine, total glucosides of white peony).

Strong CYP3A Inhibitors

Systemic use of known strong cytochrome P450 3A (CYP3A) inhibitors (includes over-the-counter or prescription medicines, vitamins and/or herbal supplements) is not permitted from Screening through

the end of study drug administration. [Table 1](#) includes examples of commonly used strong CYP3A inhibitors. In addition, herbal therapies and other traditional medicines with unknown effects on CYP3A are not permitted from Screening through the end of study drug administration.

Table 1. Examples of Commonly Used Strong CYP3A Inhibitors

Strong CYP3A Inhibitors
Boceprevir
Cobicistat
Clarithromycin
Conivaptan
Grapefruit (fruit or juice)
Indinavir
Itraconazole
Ketoconazole
Lopinavir/Ritonavir
Mibefradi
Nefazodone
Nelfinavir
Posaconazole
Ritonavir
Saquinavir
Telaprevir
Telithromycin
Troleandomycin
Voriconazole

CYP3A = cytochrome P450 3A

5.4 Prior and Concomitant Therapy

Aminosalicylates, immunomodulators, CD-related antibiotics: Dose adjustment is prohibited during the Induction Period, the Re-Induction Period, and after Week 28 of the Maintenance Period except in the event of moderate-to-severe treatment-related toxicities and after discussion with the AbbVie Therapeutic Area Medical Director (TA MD) or if subject meets protocol defined rescue criteria. All subjects receiving CD-related antibiotics may discontinue treatment after the Induction Period or Re-Induction Period at the discretion of the investigator. Subjects who continue CD-related antibiotics at Week 0 of the Re-Induction Period will maintain their CD-related antibiotics and respective doses through the Re-Induction Period. CD-related antibiotics may be initiated at any time for the treatment of an AE.

Inhaled glucocorticoids: Subjects may take inhaled glucocorticoids if used for a stable medical condition and at stable dose \geq 4 weeks prior to the Baseline Visit (Week 0, Day 1 of the Induction Period). Short-term use (\leq 14 days) of an inhaled glucocorticoid at an increased dose/frequency for treatment of an AE unrelated to CD is permissible.

Use of concomitant biologic therapies for indications other than CD (e.g., denosumab or intravitreal administration of VEGF inhibitors such as brolucizumab) may be approved by the AbbVie TA MD on a case-by-case basis.

Any medication (including over-the-counter or prescription medicines, vitamins, and/or herbal supplements) that the subject is receiving at the time of enrollment or receives during the study must be recorded from 30 days prior to study drug administration through the post-treatment visit (70-day follow-up visit).

Any questions regarding concomitant or prior therapy should be raised to the AbbVie TA MD. Information regarding potential drug interactions with ABBV-154 can be located in the ABBV-154 Investigator's Brochure.

Subjects must be able to safely discontinue any prohibited medications as specified in eligibility criteria in Section 5.1 or 5 half-lives or 4 weeks, whichever is longer, prior to initial study drug administration. Subjects must be consented for the study prior to discontinuing any prohibited medications for the purpose of meeting study eligibility.

Vaccines

If the subject and investigator choose to receive/administer live vaccines with replicating potential, these vaccinations must be completed (per local label) at least 28 days (or longer if required locally) before first dose of study drug. Live vaccines (except non-replicating live vaccines – e.g., JYNNEOS monkeypox vaccine) are prohibited during the study and for at least 70 days after the last dose of study drug. Examples of live vaccines with replicating potential include, but are not limited to, the following:

- Monovalent live influenza A (H1N1) (intranasal);
- Seasonal trivalent live influenza (intranasal);
- Zostavax (herpes zoster, live attenuated);
- Rotavirus;
- Varicella (chicken pox);
- Measles-mumps-rubella or measles-mumps-rubella-varicella;
- Oral polio vaccine;
- Smallpox/monkeypox vaccine capable of replicating (ACAM2000®);
- Yellow fever;
- Bacille Calmette-Guérin (BCG);
- Typhoid (oral).

Administration of inactivated (non-live) vaccines is permitted prior to or during the study according to local practice guidelines. Examples of common vaccines that are inactivated, toxoid, or biosynthetic include, but are not limited to the following: injectable influenza vaccine, pneumococcal, Shingrix (zoster vaccine, recombinant, adjuvanted), and pertussis (Tdap) vaccines.

COVID-19 Pandemic-Related Vaccination Guidance

Given the ongoing COVID-19 pandemic, selected non-live vaccines (e.g., mRNA, non-replicating viral vector, protein subunit, etc.) to prevent SARS-CoV-2 infection may be administered during screening or the treatment period, as long as components of the vaccine are not contraindicated.

The decision to receive a locally available vaccine should be based on local guidance and an individual discussion between the treating physician and the subject.

The potential impact of ABBV-154 on SARS-CoV-2 vaccination is unknown. Therefore, study drug should be administered as follows:

- The first dose of study drug, when possible, is preferred to be given at least ± 7 days from the SARS-CoV-2 vaccine administration.

Note: The above guidance applies to all SARS-CoV-2 vaccine doses given as part of the complete treatment course.

These recommendations may be subject to change based on the evolving knowledge around the use of SARS-CoV-2 vaccines and as more data are collected in real-world scenarios and clinical trials.

Any SARS-CoV-2 vaccine information must be documented on the COVID-19 vaccine electronic case report form (eCRF). Refer to the Operations Manual for instructions on reporting any AEs associated with the COVID-19 vaccine.

Rescue Concomitant Medications/Therapy

Unless qualifying for Rescue Therapy or undergoing mandatory tapering for glucocorticoids as described below, no changes may be made to oral glucocorticoids, aminosaliclates, or immunomodulators during the Induction and Re-Induction Periods, or after Week 28 of the Maintenance Period.

In the Induction Period, starting at or after the completion of the Week 8 Visit and thereafter (Week 8 through Week 12), subjects who demonstrate inadequate response as defined below may receive Rescue Therapy with oral glucocorticoids (≤ 20 mg/day prednisone or equivalent, ≤ 9 mg/day budesonide, or ≤ 5 mg/day beclomethasone). Changes in aminosaliclates, or immunomodulators are not permitted during the Induction Period.

In the Maintenance Period, starting at or after the completion of the Week 4 Visit and thereafter (Week 4 through Week 40), subjects who demonstrate inadequate response as defined below will be eligible to receive rescue therapy with a single dose of ABBV-154 600 mg IV at the respective visit, followed by ABBV-154 230 mg SC after 2 weeks and EOW thereafter.

In the Maintenance Period, subjects who have received rescue therapy with ABBV-154 for at least 4 weeks and who continue to demonstrate inadequate response, as defined below, may receive

additional rescue therapy with oral glucocorticoids (≤ 20 mg/day prednisone or equivalent, ≤ 9 mg/day budesonide, or ≤ 5 mg/day beclomethasone), aminosaliculates, or immunomodulators.

In the Induction Period after the Week 8 Visit and in the Maintenance Period after the Week 4 Visit, inadequate response may also be confirmed at unscheduled visits and visits where collection of CDAI components was not planned.

Rescue Therapy is not permitted in the Re-Induction Period.

Subjects who receive protocol-defined glucocorticoid Rescue Therapy, initiate glucocorticoids (other than inhaled) after Baseline without qualifying for Rescue Therapy, fail to complete glucocorticoid tapering by Week 6, or who increase doses of or initiate treatment with aminosaliculates or immunomodulators during the Induction Period will be considered non-responders and will be re-randomized into the Re-Induction Period. All subjects who fulfill the clinical response AND/OR endoscopic response (per local read) definition at Week 12 of the Re-Induction Period will be re-randomized into the Maintenance Period.

The criteria for inadequate response are the following:

- Induction Period: Presence of clinical symptoms defined as CDAI ≥ 220 and not achieving a decrease in CDAI ≥ 35 points from Baseline of the Induction Period.
- Maintenance Period: Presence of clinical symptoms defined as CDAI ≥ 220 and an increase in CDAI ≥ 70 points from Baseline of the Maintenance Period.
- And, for both the Induction Period and Maintenance Period, presence of at least 1 of the following objective markers of inflammation:
 - hs-CRP \geq ULN, and worse than the lowest value assessed during the study, or
 - FCP ≥ 250 $\mu\text{g/g}$, and worse than the lowest value assessed during the study, or
 - SES-CD, excluding the narrowing component, ≥ 6 (≥ 4 for isolated ileal disease), as scored by the site investigator at an endoscopy.

The last available values for hs-CRP and FCP will be used for assessment of inadequate response.

Use of Rescue Therapy in subjects who qualify is at the investigator's discretion and not mandatory.

5.5 Withdrawal of Subjects and Discontinuation of Study

AbbVie may terminate this study prematurely at any time, either in its entirety or partially (discontinue one or more treatment groups) or at any site. The study may be discontinued or terminated in case of an unacceptable risk, any relevant toxicity, or a negative change in the risk/benefit assessment. This might include the occurrence of AEs with a character, severity or frequency that is new in comparison to the existing risk profile. In addition, data derived from other clinical trials or toxicological studies which negatively influence the benefit-risk assessment might cause discontinuation or termination of the study. The investigator may also stop the study at his/her site if he/she has safety concerns. If AbbVie terminates the study for safety reasons, AbbVie will promptly notify the investigator. Advance notice is not required by either party if the study is stopped due to safety concerns.

A subject may voluntarily withdraw from the study at any time for any reason. An investigator may discontinue a subject's participation at any time for any reason. The AbbVie TA MD may mandate individual subject discontinuation from study drug in case of a safety concern.

Subjects must have study drug discontinued immediately if any of the following occur:

- Abnormal laboratory result or AE that meets the criteria for discontinuation of study drug as stated in Section 6.2, or rule out safe continuation of the study drug, as determined by the investigator or the AbbVie TA MD.
- Serious infection (e.g., sepsis) that cannot be adequately controlled within 2 weeks by anti-infective treatment or would put the subject at risk with continuation of study drug.
- Subject is noncompliant with TB prophylaxis (if applicable) or develops active TB at any time during the study.
- Malignancy or high-grade dysplasia of the gastrointestinal tract, except for localized NMSC or carcinoma in-situ of the cervix.
- The subject develops an anaphylactic reaction or anaphylactic shock.
- The investigator believes it is in the best interest of the subject.
- The subject requests withdrawal from study drug or the study.
- Eligibility criteria violation was noted after the subject started study drug and continuation of the study drug would place the subject at risk.
- Introduction of prohibited medications or dosages and continuation of the study drug would place the subject at risk.
- The subject becomes pregnant while on study drug.
- Subject is significantly noncompliant with study procedures, which would put the subject at risk for continued participation in the trial as determined by the investigator or AbbVie TA MD.
- Subject is prematurely unblinded to study drug assignment by the investigator or AbbVie TA MD.

State of Emergency or Pandemic-Related Acceptable Protocol Modification

During states of emergency or pandemic situations, it might be necessary to employ mitigation strategies to enable the investigator to ensure subject safety and continuity of care. Acceptable mitigation strategies are identified and included in the Operations Manual in [Appendix F](#).

The investigator should contact the AbbVie TA MD before discontinuing a subject from the study for a reason other than described in the protocol to ensure all acceptable mitigation steps have been explored.

5.6 Follow-Up After Subject Discontinuation of Study Drug or from Study

Discontinuation of Study Drug and Continuation of Study Participation

To minimize missing data for efficacy and safety assessments, subjects who prematurely discontinue study drug treatment should be encouraged to continue to be followed for all regularly scheduled visits as outlined in the Protocol Activities tables in the Operations Manual ([Appendix F](#), Section 2) and adhere to all study procedures except for administration of study drug, endoscopy, annual TB testing, PK, and plasma/serum or other biomarker or exploratory research sample collection unless a subject decides to discontinue study participation entirely (withdrawal of informed consent). Subjects should continue to be advised on the scientific importance of their data even if they discontinue treatment with study drug early. Following the discontinuation of study drug, the subject should be treated in accordance with the investigator's best clinical judgment irrespective of whether the subject decides to continue participation in the study.

In addition, a 70-Day Follow-up Visit after the last dose of study drug is required to ensure all treatment-emergent AEs/SAE have been resolved. All attempts must be made to determine the date of the last study drug dose and the primary reason for discontinuation of study drug or study participation. This information will be recorded on the appropriate eCRF page. For subjects who discontinue study drug but continue study participation, the 70-Day Follow-up Visit is not required if at least one visit has occurred at least 70 days since the last dose of study drug.

Premature Discontinuation of Study (Withdrawal of Informed Consent)

If a subject prematurely discontinues study participation (withdrawal of informed consent), the procedures outlined for the Premature Discontinuation visit should be completed as soon as possible, preferably within 2 weeks, and preferably prior to initiation of another therapy.

For subjects to be considered lost to follow-up, reasonable attempts must be made to obtain information on the subject's final status. At a minimum, 2 telephone calls must be made, and 1 certified letter must be sent and documented in the subject's source documentation.

If a subject withdraws from study follow up or withdraws permission for the collection of their personal data, the study staff may still use available public records to obtain information about survival status only, as appropriate per local regulations.

In the event a subject withdraws consent from the clinical study, biomarker research will continue unless the subject explicitly requests analysis to be stopped. When AbbVie is informed the subject has withdrawn and no longer wishes biomarker samples research to continue, samples will not be analyzed, and no new biomarker analysis data will be collected for the withdrawn subject or added to the existing data or database(s). A subject may withdraw consent for biomarker research at any time and remain in the clinical study. Data generated from clinical study and/or biomarker research, before subject withdrawal of consent, will remain part of the study results.

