3 OBJECTIVES AND ENDPOINTS

3.1 Objectives, Hypotheses, and Estimands

Primary

The primary objective of the study is to assess the efficacy, safety, and tolerability of ABBV-154 in comparison with placebo in subjects with moderately to severely active CD who had inadequate response to or were intolerant of prior biologics.

- **Primary Efficacy Objective:** The primary efficacy objective of the study is to demonstrate a higher rate of endoscopic response after 12 weeks of treatment with ABBV-154 when compared to placebo in subjects with moderately to severely active CD who had inadequate response to or were intolerant of prior biologics.

The hypothesis corresponding to the primary efficacy objective is the proportion of subjects achieving endoscopic response with ABBV-154 is greater than that with placebo at Week 12. The estimand for the primary endpoint is defined as the difference in the proportion of subjects that achieve endoscopic response at Week 12 without use of concomitant medication that could confound the efficacy (see Section 7.3) and regardless of premature discontinuation of study drug, in each of the ABBV-154 dose groups compared with the placebo group in subjects with moderately to severely active CD who had inadequate response to or were intolerant of prior biologics.

- **Secondary Efficacy Objectives:** The secondary efficacy objectives of the study are to demonstrate greater efficacy with ABBV-154 treatment when compared with placebo treatment with respect to the secondary endpoints specified in Section 3.3, in subjects with moderately to severely active CD who had inadequate response to or were intolerant of prior biologics.
- The estimands corresponding to the secondary efficacy endpoints are as follows:
 - For endpoints in the Induction Period: The difference in the proportion of subjects that achieve a response without use of concomitant medication that could confound the efficacy (see Section 7.3) and regardless of premature discontinuation of study drug, in each of the ABBV-154 dose groups compared with the placebo group in subjects with moderately to severely active CD who had inadequate response to or were intolerant of prior biologics.

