7.3 Handling Potential Intercurrent Events for the Primary and Secondary Endpoints

Primary endpoint/Categorical secondary endpoints in the Induction Period:

- Subjects will be considered as not achieving response after receiving medications that could confound the assessment of efficacy, including protocol-defined Rescue Therapy for the Induction Period, initiating glucocorticoids after Baseline, failing to complete glucocorticoid taper by Week 6, and initiating/increasing doses of aminosalicylates or immunomodulators.
- Available data collected after study drug discontinuation will be used until the initiation of medications that could confound the assessment of efficacy.

Categorical secondary endpoints in the Maintenance Period:

- Subjects will be considered as not achieving response after receiving medications that could confound the assessment of efficacy, including protocol-defined Rescue Therapy for the Maintenance Period.
- Available data collected after study drug discontinuation will be used until the initiation of medications that could confound the assessment of efficacy.

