2.0 Study Design and Objectives

2.1 Objectives, Hypotheses and Estimands

The objective of Study M20-371 is to assess the efficacy, safety, and tolerability of ABBV-154 in comparison with placebo in subjects with moderately to severely active Crohn's Disease (CD) who had inadequate response to or were intolerant of prior biologics.

Primary Efficacy Objective

The primary efficacy objective of Study M20-371 is to demonstrate a higher rate of endoscopic response after 12 weeks of treatment with ABBV-154 when compared to placebo in subjects with moderately to severely active CD who had inadequate response to or were intolerant of prior biologics.

Hypothesis corresponding to the primary efficacy objective is:

- The proportion of subjects achieving endoscopic response (see Section 3.0) with ABBV-154 is greater than that with placebo at Week 12 in the Induction Period.

The estimand corresponding to the primary efficacy objectives are defined as follows:

- The difference in the proportion of subjects that achieve endoscopic response at Week 12 without use of concomitant medication that could confound the efficacy (see Section 8.1) and regardless of premature discontinuation of study drug (see Section 8.2), in each of the ABBV-154 dose groups compared with the placebo group in subjects with moderately to severely active CD who had inadequate response to or were intolerant of prior biologics.

Secondary Efficacy Objectives

The secondary efficacy objectives of the Study M20-371 are to demonstrate greater efficacy with ABBV-154 treatment when compared with placebo treatment with respect to the secondary endpoints specified in Section 3.2, in subjects with moderately to severely active CD who had inadequate response to or were intolerant of prior biologics.

Hypotheses corresponding to the ranked secondary efficacy objectives are: for each of the secondary endpoints specified in Section 3.2, greater proportion of subjects with improvement is achieved with ABBV-154 when compared to that of placebo.

The estimands corresponding to the secondary efficacy objectives are defined for each of the secondary endpoints as follows:

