- For endpoints in the Induction Period: The difference in the proportion of subjects that achieve response/remission without use of concomitant medication that could confound the efficacy (see Section 8.1) and regardless of premature discontinuation of study drug (see Section 8.2), in each of the ABBV154 dose groups compared with the placebo group in subjects with

moderately to severely active CD who had inadequate response to or were intolerant of prior biologics.

- For endpoints in the Maintenance Period: The difference in the proportion of subjects that achieve response/remission without use concomitant medication that could confound the efficacy (see Section 8.1) and regardless of premature discontinuation of study drug (see Section 8.2), in each of the ABBV154 dose groups compared with the placebo group in subjects with moderately to severely active CD who had inadequate response to or were intolerant of prior biologics and achieved response after the 12-week induction treatment with ABBV-154.

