8.1 Intercurrent Event 1 (IE1): CD-Related Confounding Medications

The CD-related confounding medications intercurrent event is defined as follows.

In the Induction Period:

1. Initiation of protocol-defined Rescue Therapy for the Induction Period;
2. Initiation of glucocorticoids after Baseline of the Induction Period;
3. Fail to complete glucocorticoid taper by Week 6 of the Induction Period;
4. Initiation/increasing doses of aminosaliclates or immunomodulators.

In the Maintenance Period:

- Initiation of protocol-defined Rescue Therapy for the Maintenance Period.

Within each period, the time point of the CD-related confounding medications intercurrent event is defined as the date when one of the scenarios above occurs for a subject.

Binary endpoints: A composite strategy will be used in the efficacy analysis: the subject will be considered as non-responders at all visits on/after the CD-related confounding medications intercurrent event.

Continuous endpoints: A hypothetical strategy will be used in the efficacy analysis. Data collected on/after the initiation of CD-related confounding medications will not be used in the analysis. Efficacy analysis will be handled by using corresponding statistical models (e.g., the Mixed-Effect Model Repeated Measurement [MMRM] model).

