8.2 Intercurrent Event 2 (IE2): Premature Discontinuation of Study Drug

Following the intent-to-treat (ITT) principle, a treatment policy strategy will be used to handle the IE2. Data collected on/after premature discontinuation of study drug will be used for all efficacy endpoints.

The only exception is when data are collected on/after the date subjects switching to other treatments for CD, which will be handled as follows:

- **Binary endpoints:** A composite strategy will be used in the efficacy analysis: the subject will be considered as non-responder at all visits after the initiation of other CD-related treatments.
- **Continuous endpoints:** A hypothetical strategy will be used in the efficacy analysis. Data collected after the initiation of other CD-related treatments will not be used in the analysis. Efficacy analysis will be handled by using corresponding statistical models (e.g., MMRM model).

The other CD-related medications include:

- Biologics approved for CD (Adalimumab, Certolizumab, Infliximab, Ustekinumab, Vedolizumab, Natalizumab)
- Any investigational compound
- Systemic glucocorticoids and rectal glucocorticoids
- Immunomodulators

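### The endoscopic estimands are said to hold regardless of drug discontinuation, but endoscopy is not required after discontinuation, so for these endpoints the plan largely delivers a composite strategy

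*Protocol*

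**What the plan says.** **Estimand.** Protocol 3.1 defines the primary endoscopic estimand "regardless of premature discontinuation of study drug, in each of the ABBV-154 dose groups compared with the placebo group", and uses the same phrase for the Maintenance Period endpoints, which include endoscopic response at Week 40. SAP 2.1 repeats it: "regardless of premature discontinuation of study drug (see Section 8.2), in each of the ABBV-154 dose groups compared with the placebo group".

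**Handling of discontinuation.** SAP 8.2 names a treatment policy strategy: "Data collected on/after premature discontinuation of study drug will be used for all efficacy endpoints". The exception is data obtained once the subject has switched to another CD treatment. Protocol 7.3 puts it this way: "Available data collected after study drug discontinuation will be used until the initiation of medications that could confound the assessment of efficacy". SAP Tables 1 and 2 say the same in the intercurrent-event column, for endoscopic and symptom endpoints alike.

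**Data collection.** Protocol 5.6 sets out to limit missing efficacy data by keeping subjects who stop drug in follow-up. It asks them to "adhere to all study procedures except for administration of study drug, endoscopy, annual TB testing, PK" and plasma, serum or other biomarker samples. Endoscopy is thus exempted; the CDAI components and the diary are not.

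**Missing assessments.** Under SAP 9.2.1, a subject with no evaluation in the visit window is a non-responder in NRI-C, unless the gap is due to COVID-19, which goes to multiple imputation. NRI-NC drops that exception. In the AO analysis (SAP 9.2.3) a subject without the assessment is left out. SAP 9.3.3 and 9.4.2 nevertheless describe AO as using all data after both intercurrent events.

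**The concern.** A treatment policy strategy targets the outcome as it stands after the intercurrent event, so that outcome has to be observed or credibly imputed. Endoscopy is the only source of the primary endpoint, and it is the assessment that subjects who stop drug are excused from. The gap is filled by a rule that sets them to non-response. Treating an intercurrent event as failure is a composite strategy, so the label and the analysis describe different quantities.

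Three things follow if this is left as written:

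- The primary result would be reported with a property that the design does not generally support.
- Table 2 would cover two different questions under one description at Week 40: symptom endpoints observed after discontinuation, and an endoscopic endpoint mostly not.
- No planned analysis would show how much the substitution matters, because NRI-NC makes the same one and AO removes the subjects.

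**Working it through.** **Who is affected.** Setting Protocol 5.6 and 7.3 beside SAP 8.1, 8.2 and 9.2.1, a subject must meet all of these conditions: stops study drug; stays in the study; starts no medication that already makes the subject a non-responder by rule; and has no endoscopy in the Week 12 or Week 40 window. In NRI-C the gap must also not be due to COVID-19. The reported rate changes only if that subject would have responded.

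**How each analysis treats such a subject**

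| Analysis | Endoscopic response | CDAI, SF/AP |
|---|---|---|
| NRI-C (main) | Non-responder | Observed value used if collected |
| NRI-NC (sensitivity) | Non-responder | Observed value used if collected |
| AO (supplementary) | Excluded | Observed value used if collected |

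**The plan's own power figures.** Inputs from Protocol 7.10 and SAP 2.4: placebo 11%, difference 26 points (so ABBV-154 37%), two-sided alpha 0.10, 53 per group at Week 12 and 40 per group at Week 40. With mean rate 0.24 and z = 1.645:

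power = Φ{[0.26 − 1.645·√(2·0.24·0.76/n)] / √[(0.11·0.89 + 0.37·0.63)/n]}

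- n = 53: Φ[(0.26 − 0.1365)/0.0790] = Φ(1.563) = 94.1%; stated as more than 90%.
- n = 40: Φ[(0.26 − 0.1571)/0.0910] = Φ(1.131) = 87.1%; stated as more than 80%.

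Both statements reproduce.

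**Weight of one affected would-be responder** (unstratified)

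| | Week 12 (n = 53) | Week 40 (n = 40) |
|---|---|---|
| Change in that arm's rate | 1/53 = 1.9 points | 1/40 = 2.5 points |
| Difference if on ABBV-154 | 26.0 − 1.9 = 24.1 | 26.0 − 2.5 = 23.5 |
| Difference if on placebo | 26.0 + 1.9 = 27.9 | 26.0 + 2.5 = 28.5 |
| Difference if one in each arm | 26.0 | 26.0 |

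**Range over an assumed share.** The documents give no discontinuation rate, so the following shares are assumptions. Take 11% and 37% as the true rates regardless of discontinuation. Let a share q of each arm be affected, and let those subjects respond at their arm's own rate. Each scored rate is then the true rate times (1 − q), and the difference is 26.0·(1 − q).

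| q in both arms | Difference | Power, n = 53 | Power, n = 40 |
|---|---|---|---|
| 5% | 24.7 | 92.7% | 84.9% |
| 10% | 23.4 | 91.0% | 82.6% |
| 20% | 20.8 | 86.7% | 77.1% |
| 30% | 18.2 | 81.3% | 70.8% |

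If affected subjects respond at half their arm's rate, q = 20% gives 26.0·(1 − 0.10) = 23.4 points and 91.0% power at n = 53.

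**Unequal shares (n = 53)**

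- 5% on placebo, 20% on ABBV-154: 0.37·0.80 − 0.11·0.95 = 29.60% − 10.45% = 19.2 points.
- 20% on placebo, 5% on ABBV-154: 0.37·0.95 − 0.11·0.80 = 35.15% − 8.80% = 26.4 points.
- 20% on placebo, 5% on ABBV-154, with a true 37% in both arms: 0.37·(0.95 − 0.80) = 5.6 points, and the two-sided rejection rate rises from 10% to about 16%.
- The same shares with a true 11% in both arms: 1.7 points and about 11%.

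The last two differences are spurious only against a treatment policy target. Under a composite target they are part of the effect, which is why the label matters.

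**The case against.** **The operative sentences are not false.** Protocol 7.3 speaks of available data, and SAP 8.2 and the AO text of data collected. Each stays literally true if few endoscopies exist. Non-responder imputation is openly prespecified and is no fault in itself. This stands as far as it goes, but a sentence about using whatever was collected does not support an estimand said to hold regardless of discontinuation.

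**Endoscopies may exist.** The activity schedules in Protocol Appendix D tick endoscopy at the Premature Discontinuation visit in all three periods. Section 5.6 excuses subjects from endoscopy without forbidding it. However, 5.6 describes that visit for withdrawal from the study, to be done "preferably within 2 weeks, and preferably prior to initiation of another therapy", so it is not tied to Week 12 or Week 40. The Operations Manual tables and the visit windows are not in the supplied text. A reader might infer that no endoscopy will ever be available after discontinuation; the documents do not support that, and some subjects may have one in the window.

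**The group may be small.** Several conditions must hold at once, and this is a Phase 2b dose-ranging study without overall Type I error control. That is fair, and it limits the point to description and sensitivity.

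**The estimand should not be defined by missingness.** Writing the imputation rule, with its COVID-19 exception, into the estimand would merge what the SAP keeps apart in 8.0 and 9.2. This is right, and the fix respects it.

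**Conclusion.** The passages conflict and should be reconciled. For endoscopic response, including the primary endpoint, the plan claims a treatment policy for drug discontinuation but largely implements a composite one, because the assessment is not required once drug is stopped.

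The size is not known. One affected would-be responder weighs 1.9 points at Week 12 and 2.5 at Week 40. Beyond that, everything depends on how many such subjects there are, in which arms, and whether they would have responded. The shift is zero if none would have, or if equal numbers per arm cancel.

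A reader might go further and conclude that the primary comparison is biased in a known direction, or that the trial is underpowered. The documents support neither. They give no discontinuation rate, and the shift can go either way. The stated power reproduces, and the planned 37% may already count such subjects as non-responders. The reductions under working rest on assumed shares and on taking 11% and 37% as rates regardless of discontinuation.

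Subjects who leave the study altogether are outside the 5.6 exemption and are not part of this conflict.

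**What to change.** For endoscopic endpoints only:

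1. **Estimand and intercurrent-event text** (Protocol 3.1 and 7.3; SAP 2.1, 8.2, Tables 1 and 2). Remove the unqualified statement that the result holds regardless of discontinuation, and the treatment policy label. Say that, because endoscopy is not required after discontinuation, the result largely reflects a composite strategy, and that any in-window endoscopy obtained before other CD medication is still used. Keep the present wording for CDAI and SF/AP.
2. **Missing-data rules** (SAP 9.2). Leave NRI-C, the COVID-19 imputation and the override list as they are, and keep them out of the estimand definition. Adding discontinuation itself to the override list would discard observed endoscopies and the COVID-19 exception.
3. **AO description** (SAP 9.3.3 and 9.4.2). Note that AO may contain few or no endoscopies after discontinuation.
4. **One added sensitivity analysis.** For subjects who discontinued and have no in-window endoscopy, vary the assumed response separately by arm, for example as a tipping-point analysis, and report where the conclusion changes. NRI-NC cannot do this because it holds that response at zero in every arm.

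The cost is a slightly less general estimand statement and a little more analysis work. No NRI-C or NRI-NC classification changes, and no procedure, visit or subject is added. Collecting endoscopy after discontinuation would also remove the conflict, but it changes a study procedure; that is the sponsor's decision and is not proposed here.
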